### **Recruitment routes and measures**

Healthy volunteers will be informed about the possibility to participate in the study. If they are willing to participate, they will be fully informed about objectives and methods (especially about the scientific/explorative character of the study), benefits and risks and the revocability of their participation in the study.

## 10. Study course

[figure not shown]
### Procedure for informing about and obtaining consent

Participants can only be included in the study after a written declaration of consent has been given. The written declaration of consent requires that the volunteers are informed orally and in written form about the objectives and methods (including the scientific-explorative character of the study), benefits and risks as well as the revocability of their participation in the study. The information is provided by means of comprehensible proband information sheets. By giving their written consent, the volunteers declare that they agree to the collection and storage of data relevant to the study and their verification by monitoring or authorities. It must be clearly communicated to the study participant that a withdrawal of consent is possible at any time and without any disadvantage. Furthermore, all study participants/test persons are informed that this study is a purely scientific study without any current diagnostic or therapeutic benefit.

The original of the consent form is kept in the study folder at the study site. The volunteer receives a copy of the patient information and consent form. The proband information and the consent form can be found in the appendix of this study protocol.

### Measurements

[figure not shown]
After informing of the subjects, all study participants are imaged by MSOT at 3 positions of 2 anatomical muscle regions on both sides (right and left): upper/lower leg, on predefined muscle groups (leg proximal: Musculus quadriceps, distal: Musculus gastrocnemius). The examination is performed by two independent examiners directly one after the other. The examination is performed analogous to sonography over the corresponding skin layers without further invasive procedures. The anatomical region can be localized by means of built-in B-scan sonography; the corresponding optoacoustic signals can be recorded in parallel. Each examiner performs two repetitive scans per muscle position. The duration per anatomical region is limited to 5 minutes; this corresponds to a maximum of 20 minutes for both lower extremities. The subjects can remain in a relaxed body position during the examination; assistance in the form of breathing manoeuvres or similar is not necessary. Subsequently, a 6-minute walk test is performed to test muscle activation. Afterwards another examination with MSOT is carried out analogous to the above mentioned procedure. The same procedure is repeated after 14 days.

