### Primary/secondary objectives and/or hypotheses

#### *Hypotheses:*

- The quantitative amount of hemo/myoglobin signal in muscles of healthy volunteers determined by MSOT differs *before and after the 6-minute walk test*.
- The quantitative amount of oxygenated/deoxygenated hemo/myoglobin signal in muscles of healthy volunteers determined by the MSOT differs *before and after the 6-minute walk test*.
- The quantitative amount of collagen signal in muscles of healthy volunteers determined by MSOT does not differ *before and after the 6-minute walk test*.
- The quantitative amount of hemo/myoglobin signal in muscles of healthy volunteers determined by the MSOT does not differ when *the follow-up is measured after 2 weeks*.
- The quantitative proportion of oxygenated/deoxygenated hemo/myoglobin signal in muscles of healthy volunteers determined by MSOT does not differ when *the follow-up is measured after 2 weeks*.
- The quantitative proportion of collagen signal in muscles of healthy volunteers determined by MSOT does not differ when *the follow-up is measured after 2 weeks*.
- The quantitative proportion of hemo/myoglobin signal in muscles of healthy volunteers determined by MSOT does not differ *within a muscle* of healthy volunteers.
- The quantitative proportion of oxygenated/deoxygenated hemo/myoglobin signal determined by MSOT does not differ *within one muscle* of healthy volunteers.
- The quantitative fraction of collagen signal determined by MSOT does not differ *within one muscle* of healthy subjects.
- The quantitative amount of hemo/myoglobin determined by MSOT does not differ *between two measurements by the same examiner*.
- The quantitative amount of oxygenated/deoxygenated hemo/myoglobin determined by the MSOT does not differ *between two measurements by the same examiner*.
- The quantitative amount of collagen determined by the MSOT does not differ *between two measurements by the same examiner*.
- The quantitative amount of hemo-/myoglobin determined by the MSOT does not differ *between measurements made by two different examiners*.

- The quantitative amount of oxygenated/deoxygenated hemo-/myoglobin determined by the MSOT does not differ *between measurements performed by two different examiners*.
- The quantitative amount of collagen determined by the MSOT does not differ *between measurements made by two different examiners*.

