**Primary objective:**

- Comparison of the quantitative proportion of hemo/myoglobin and collagen signal in muscle tissue of healthy subjects before and after physical exercise (6-MWT) determined by MSOT, as well as over time.

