**Secondary objectives:**

- Comparison of the quantitative amount of hemo/myoglobin and collagen signal determined by MSOT in muscle tissue of healthy volunteers at timepoint 1 and timepoint 2 after two weeks
- Comparison of the quantitative proportion of oxygenated/deoxygenated hemo/myoglobin signal in muscle tissue of healthy volunteers at timepoint 1 and timepoint 2 after two weeks
- Comparison of the MSOT-determined quantitative amount of hemo/myoglobin and collagen signal at three muscle positions of two muscles (quadriceps femoris and gastrocnemius)
- Comparison of the quantitative proportion of oxygenated/deoxygenated hemo/myoglobin signal determined by MSOT in three muscle positions of two muscles (quadriceps femoris and gastrocnemius)
- Comparison of the quantitative proportion of hemo/myoglobin and collagen signal determined by MSOT in muscle tissue of healthy female and male volunteers
- Comparison of the quantitative proportion of oxygenated and deoxygenated hemo/myoglobin signals determined by MSOT in muscle tissue of healthy female and male volunteers
- Correlation of the hemo/myoglobin and collagen signal determined with MSOT with the 6-MWT
- Correlation of the oxygenated/deoxygenated hemo/myoglobin signal determined by MSOT with the 6-MWT
- Comparison of the quantitative amount of hemo/myoglobin and collagen signal determined by MSOT between two independent examiners

- Comparison of the quantitative amount of hemo/myoglobin and collagen signal determined by MSOT between two images of one examiner

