## Recording of target parameters

- Non-invasive in-vivo measurement of hemo/myoglobin, collagen and lipid content/signal and oxygenation by MSOT
- Assessment of the 6-minute walk test
- Determination of routine data (height, weight, underlying diseases, medication)

Time schedule and study duration for the individual volunteer:

The duration of the study participation is about 125 minutes for the individual volunteer. At timepoint 1 the duration of study participation is 75 minutes. Approximately 20 minutes are allotted for the education of study participants, approximately 5 minutes for the collection of routine clinical data, 10 minutes for clinical (routine) testing using 6-MWT, and 40 minutes for the actual examination. At timepoint 2, participation time for the study is about 50 minutes. The clinical (routine) test using 6-MWT takes 10 minutes, and 40 minutes for the actual examination.

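### After the walk, time since exercise can pass for an examiner, region or position difference, because the readable plan fixes neither a balanced scan order nor which scans feed each reproducibility comparison

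*Protocol*

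**What the plan says.** Protocol section 10 (Measurements) has each volunteer scanned at three positions of two muscles on both legs. On the examiners it says "The examination is performed by two independent examiners directly one after the other", and "Each examiner performs two repetitive scans per muscle position". On time it says "The duration per anatomical region is limited to 5 minutes; this corresponds to a maximum of 20 minutes for both lower extremities". After the walk, "Afterwards another examination with MSOT is carried out analogous to the above mentioned procedure", and everything is repeated at 14 days. The time schedule in the same section allots, for the second visit, "The clinical (routine) test using 6-MWT takes 10 minutes, and 40 minutes for the actual examination"; the first visit also has 40 minutes of examination.

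Section 8 makes the procedure the same for every volunteer and plans no randomization (that sentence concerns groups). Blinding during measurement and analysis is planned, but it does not set an order. The readable text does not say which examiner starts, when they change over, which leg, muscle or position comes first, or how soon after the walk scanning begins.

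On the expected effect, section 6 states "The quantitative amount of hemo/myoglobin signal in muscles of healthy volunteers determined by MSOT differs" before and after the walk. It says the same of the oxygenation signals, and expects no change in collagen. The primary objective is a comparison "in muscle tissue of healthy subjects before and after physical exercise (6-MWT) determined by MSOT, as well as over time". A typical secondary objective is "Comparison of the quantitative amount of hemo/myoglobin and collagen signal determined by MSOT between two independent examiners"; neither it nor the position and 2-week objectives name the walk phase. The SAP makes reproducibility across examiner, time, exercise and position the primary outcome. It averages multiple scans without saying that averaging stays within walk phase or examiner, and it has no term for order or time since the walk.

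**The concern.** The study expects exercise to move two of the signals whose reproducibility it wants to measure. If that movement subsides while the post-walk scans are being taken, a later scan sees less of it. Whoever or whatever is scanned later then looks different, although examiner and tissue may agree perfectly. A procedure identical for all volunteers, if it includes a fixed order, makes this a systematic shift. An order that varies haphazardly would mainly add noise.

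At stake are the SAP's primary outcome and the planning of later studies in children, which is the protocol's stated purpose for these data. The protection is uneven. The choice of scans for the reproducibility comparisons can be written at any time before analysis. The before/after comparison has to use post-walk scans, and an order that was not balanced during scanning cannot be balanced afterwards.

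**Working it through.** **The plan's own times.** 2 muscles × 2 legs × 5 min = 20 min per examination. Two examinations per visit (before and after the walk) give 2 × 20 = 40 min, as the schedule states. If each examiner needed 20 min, a visit would need 2 × 2 × 20 = 80 min. So one 20-minute block holds both examiners: 12 positions × 2 examiners × 2 repeats = 48 scans, or 1,200 s / 48 = 25 s each.

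**Assumptions (not in the documents).** The change equals 1 when scanning starts and decays exponentially with half-life h = 5, 10 or 20 min. The block is filled evenly from 0 to 20 min. A delay D before scanning multiplies every difference by 2^(−D/h) and leaves the ratios unchanged.

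**Formula.** Mean remaining effect in a window from a to b minutes: h / [ln 2 × (b − a)] × [2^(−a/h) − 2^(−b/h)].

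**Worked case.** One examiner finishes all regions first, h = 10. First examiner (0–10 min): 10 / (0.693 × 10) × (1 − 0.5) = 0.721. Second examiner (10–20 min): 0.721 × 0.5 = 0.361. Difference 0.361.

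**False examiner difference, as a share of the initial change:**

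| Examiners change over | h = 5 | h = 10 | h = 20 |
|---|---|---|---|
| at each position (every 50 s) | 0.039 | 0.031 | 0.021 |
| at each region (every 2.5 min) | 0.116 | 0.094 | 0.062 |
| after all regions (10 min) | 0.406 | 0.361 | 0.248 |

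Equal pooling of pre- and post-walk scans halves these figures.

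**Regions and positions.** For a lag of L minutes, the later effect divided by the earlier one is 2^(−L/h).
- Last versus first region: L = 15 min when examiners change at each position or region, giving 0.13, 0.35 and 0.59 (h = 5, 10, 20). L = 7.5 min for each examiner when one finishes first, giving 0.35, 0.59 and 0.77.
- Third versus first position: L = 3.33 min when examiners change at each position, giving 0.63 to 0.89. L = 1.67 min otherwise, giving 0.79 to 0.94.
- Two consecutive repeats 25 s apart: 0.94 to 0.99, so intra-examiner bias is small.

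**What this could do to a test.** Assume h = 10, a fixed order, post-walk scans only, and a mean exercise effect over the block equal to 1 SD of the paired examiner difference. The block mean is 0.541, so the shifts are 0.031/0.541 = 0.058 SD, 0.094/0.541 = 0.173 SD and 0.361/0.541 = 0.667 SD. A two-sided paired t-test at 0.05 with 10 pairs (noncentral t, 9 df, noncentrality √10 × shift) then declares a false examiner difference in 5%, 8% and 47% of studies. The SAP treats anatomical locations as independent. If that means 4 regions × 10 = 40 pairs with the same per-pair shift, the middle figure rises from 8% to 19%.

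**What it could do to the ICC, at the same effect.** With a true ICC of 0.80 and total SD 1, the SD of the paired difference is √(2 × 0.2) = 0.632, so the largest shift is d = 0.667 × 0.632 = 0.422. A fixed order gives an absolute-agreement ICC of 0.8 / (1 + d²/2) = 0.73. An order varied 5/5 without an order term gives (0.8 − d²/4) / (1 + d²/4) = 0.72.

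**The case against.** The strongest reply is that the order may not be missing. Figures are absent from the readable copy at the study design, at the start of the study course and directly under Measurements, which is where a sequence would be drawn. This stands: a reader might infer that the plan has no scan order, and the documents do not support that. It does not reach the second gap, because the SAP is text and does not name the scans used.

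Next, the large examiner figures need several things at once: post-walk scans, a fixed order, one examiner finishing all regions first, an assumed half-life and an assumed effect size. The 5-minute limit per region fits one continuous visit to each region at least as well, and the examiner shift is then modest. This also stands. The reassurance has two limits. The false-positive rate rises with the number of pairs if locations are analysed as independent, and the region contrast is affected under every order considered.

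Third, parts are already covered. Matched testing is planned, the post-walk examination is described as analogous and the 14-day procedure as the same. If the order really is kept, recovery largely cancels from the 2-week comparison. Raw imaging data are retained and may carry acquisition times, though the documents do not say so.

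Finally, this is an exploratory pilot. That excuses the absence of a sample-size calculation. It does not excuse leaving open which scans define the primary outcome.

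**Conclusion.** The point holds in a conditional form. The readable protocol and the SAP leave open which walk phase feeds the examiner, muscle, side, position and 2-week comparisons, and the readable text shows no counterbalanced order. If the hypothesised exercise change fades within the block, post-walk or pooled scans confound time since the walk with examiner, region and position.

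The size depends on an assumed half-life of 5 to 20 minutes and on an order the text does not give. The false examiner difference runs from 2–4% through 6–12% to 25–41% of the initial change, and the last region keeps 13–77% of the first region's effect. Pre-walk scans are untouched, as is collagen under its own hypothesis. The 2-week comparison is affected only if the order differs between visits.

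A reader might infer that the examiner comparison is invalid, or that roughly half of such studies would report a false examiner difference. The documents do not support that: the 47% belongs to one order and one set of assumptions. The change is worth making because it is nearly free and part of it cannot be made after scanning.

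**What to change.** 1. State in the SAP that pre-walk scans are the basis of the examiner, within-muscle position, between-muscle, left-right and 2-week comparisons, with post-walk scans secondary. State that scans are averaged only within walk phase, and within examiner for the examiner comparison.
2. Write the scan order down, or point to the figure if it is there. Alternate which examiner goes first, 5 and 5 across the 10 volunteers. Keep each volunteer's order the same before and after the walk and at both visits.
3. Record the start time for each examiner and region. Pair each post-walk scan with the pre-walk scan of the same location and examiner. Use order or time since the walk in a supportive analysis of the post-walk data. Alternation alone removes the mean examiner shift but leaves its spread between volunteers. It also does not separate region from time, which is why step 1 carries the region and position comparisons.

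Cost: protocol and SAP wording, an order list for 10 volunteers, and 2 examiners × 4 regions = 8 start times per session (8 × 2 sessions × 2 visits = 32 per volunteer). No extra scans or visits are needed. Post-walk scans no longer feed the main reproducibility estimates, and an order term takes 1 of the 9 degrees of freedom in a 10-volunteer post-walk examiner comparison.

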## Recording of target parameters

- Non-invasive in-vivo measurement of hemo/myoglobin, collagen and lipid content/signal and oxygenation by MSOT
- Assessment of the 6-minute walk test
- Determination of routine data (height, weight, underlying diseases, medication)

Time schedule and study duration for the individual volunteer:

The duration of the study participation is about 125 minutes for the individual volunteer. At timepoint 1 the duration of study participation is 75 minutes. Approximately 20 minutes are allotted for the education of study participants, approximately 5 minutes for the collection of routine clinical data, 10 minutes for clinical (routine) testing using 6-MWT, and 40 minutes for the actual examination. At timepoint 2, participation time for the study is about 50 minutes. The clinical (routine) test using 6-MWT takes 10 minutes, and 40 minutes for the actual examination.

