The MSOT data collected so far seem promising to enable therapy monitoring in DMD patients. Preliminary work by other groups has already demonstrated a very good precision and reproducibility of MSOT. However, it has not yet been investigated to what extent 1) previous physical activity, 2) different measurement positions of the muscle, 3) different examination dates and 4) intra- and interrater variability influence the measurement results. Especially molecular changes immediately after the 6-MWT are relevant for studies in muscle patients with DMD.

In this first pilot study, the aim is to investigate in healthy adults whether increased exercise alters haemoglobin values, the collagen content remains constant and repeated measurements at different muscle positions by different investigators provide consistent measurement results over time. This information is essential for further studies of children with neuromuscular disorders to properly evaluate a possible response to therapy.

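### The two-week comparison of pre-walk haemoglobin and oxygenation signals may be confounded with preceding activity, because the time before the first scan is budgeted differently at the two visits and no rest condition is set

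*Protocol*

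**What the plan says.** The time schedule in the protocol (section 10, Recording of target parameters) gives an overall figure, "The duration of the study participation is about 125 minutes for the individual volunteer", and divides it by visit. For the first visit it says "At timepoint 1 the duration of study participation is 75 minutes" and lists, besides 10 minutes for the walk test and 40 minutes for the examination, two preparatory items: "Approximately 20 minutes are allotted for the education of study participants, approximately 5 minutes for the collection of routine clinical data". For the second visit, of about 50 minutes, it lists only the walk and the scans: "The clinical (routine) test using 6-MWT takes 10 minutes, and 40 minutes for the actual examination".

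Section 10, Measurements, has imaging follow the informing of the subjects. It allows a relaxed body position during the examination, caps each of four regions at 5 minutes (20 minutes in all), and then says "The same procedure is repeated after 14 days". Section 7 has the routine data collected at presentation, without placing this before or after the first scan.

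The project summary (section 3) says of the MSOT readings that "it has not yet been investigated to what extent 1) previous physical activity" influences them; section 5 repeats the point. Among the hypotheses in section 6 are that haemoglobin and oxygenation signals change after a 6-minute walk, and that they do not change over two weeks. The SAP makes reproducibility across examiner, time, exercise and muscle position the primary outcome, and compares signals with a paired t-test or a Wilcoxon signed-rank test.

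**The concern.** The protocol expects six minutes of walking to alter the haemoglobin and oxygenation signals. What a volunteer did shortly before the baseline scan could then alter them too. On the written schedule, every volunteer has at least a 20-minute talk before the first scan at visit 1, and no such item appears at visit 2. The difference goes with visit number and runs the same way in everyone. A paired comparison of the two visits cannot tell it apart from change over time, and recruiting more volunteers would not remove it.

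Change over time is part of the primary objective, of two secondary objectives and of three no-difference hypotheses. A systematic shift could produce a two-week difference that is not real, or hide one that is. Recent activity before the visit 2 baseline could also narrow that visit's contrast between pre-walk and post-walk scans. The signals exposed are haemoglobin and oxygenation; the argument does not extend to collagen, which the protocol expects the walk to leave unchanged.

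**Working it through.** **1. Time budget (protocol section 10, Recording of target parameters).**

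| Item | Timepoint 1 (min) | Timepoint 2 (min) |
|---|---|---|
| Information | 20 | – |
| Routine data | 5 | – |
| 6-minute walk test | 10 | 10 |
| Examination | 40 | 40 |
| Sum | 75 | 50 |

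75 + 50 = 125, so the plan's three figures reproduce. The visits differ by 75 − 50 = 25 minutes, and 25 = 20 + 5, so the whole gap is information and data collection.

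**2. What comes before the first scan.** Section 10, Measurements, puts the 20 minutes of information before imaging. The 5 minutes of routine data are probably also before it, since section 7 has them collected at presentation, but the order is not given. The documented difference before the scan is therefore at least 20 and at most 25 minutes.

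**3. Pre-scan conditions.** The visible text of neither document sets a rest period, a posture, an activity restriction or a time of day for the first scan at either visit. The relaxed position in section 10 applies during the examination.

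**4. Which measurements are exposed.** The post-walk scans follow the same walk at both visits, so the question concerns mainly the pre-walk scans. The pre-walk examination is allowed up to 5 × 4 = 20 minutes in a relaxed position. Any carry-over would probably fade during that time and fall mainly on the regions scanned first.

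**5. Illustration of size.** The documents give no SD for the signal and no effect of rest, so the actual bias cannot be computed. Let δ be a systematic visit shift in SDs of the paired difference, with no true change over time.

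- Inputs: n = 10 (section 9); significance level 0.05 (SAP), taken as two-sided because the SAP does not say; paired t-test (SAP).
- Critical value: t(0.975; 9 df) = 2.262.
- Noncentrality: δ√n.
- Rejection probability: P(|T| > 2.262), with T noncentral t on 9 df.

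| δ (assumed) | δ√10 | Significant two-week difference |
|---|---|---|
| 0 | 0 | 5% |
| 0.25 | 0.79 | 11% |
| 0.5 | 1.58 | 29% |
| 1.0 | 3.16 | 80% |

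The estimated mean difference is biased by the full δ in each row. The calculation applies one constant shift to the compared signal; a shift confined to the first regions would matter less for the others.

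**The case against.** A reader might infer from the schedule that visit 1 gives 25 minutes of rest, that visit 2 scanning starts on arrival, and that the two-week comparison is therefore confounded. The documents do not support this. The schedule is a rounded budget of participation time. It has no line at either visit for waiting, positioning, gel or goggles, so a missing line at visit 2 does not show that scanning begins at once. Nothing says whether volunteers sit, stand or move during the talk and the data collection. Figures that may show the visit flow are missing from the text under review, and the visible text says the same procedure is repeated. All of this stands, and it limits the point to a possible confounding.

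The assumed shifts are not evidence about this trial: any paired t-test with n = 10 gives the same rates for a bias of the same size, and zero is among the possible values. That also stands.

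A further argument is that an exploratory pilot of 10 volunteers, meant to learn how activity and time affect the signal, need not settle this in advance. This carries less weight. Separating activity from time is what the pilot is for, and section 11 offers its results as a way to avoid design errors in later studies. A visit difference that could be either would be of little use there.

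**Conclusion.** The point holds as a possible confounding of the pre-walk haemoglobin and oxygenation comparison between visits. It rests on three things in the documents: a budget that differs by 25 minutes between visits, of which at least 20 precede the first scan at visit 1; no stated pre-scan rest or activity condition at either visit; and the protocol's own expectation that a short walk moves these signals.

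The size and direction of any bias are unknown. The range of 5% to 80% false two-week differences depends entirely on assumed shifts of 0 to 1.0 SD, a two-sided test and no true change. Activity before arrival is uncontrolled at both visits. The unequal schedule is one concrete way in which this could become systematic instead of merely adding noise.

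**What to change.** In section 10, Measurements, require the same fixed rest period, in the same position, immediately before the first pre-walk scan at both visits. Book each volunteer's two visits at a similar time of day, since neither document holds it constant. Then update the participation times in section 10, Recording of target parameters.

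The cost depends on the length chosen and on whether the visit 1 talk is held in the resting position and runs directly up to the scan:

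- If it is, and 25 minutes is chosen, only visit 2 lengthens: 125 + 25 = 150 minutes per volunteer, or 10 × 25 = 250 minutes (about 4 hours) over the study.
- If it is not, both visits lengthen: up to 125 + 50 = 175 minutes per volunteer, or 10 × 50 = 500 minutes (about 8 hours).
- A shorter rest costs proportionately less, because what matters for this comparison is that the two visits match.

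Booking becomes slightly less flexible. This is a cheap improvement, and it closes the gap whether or not the bias is real.
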